**CCI**

**CCI**

#### **12.4.2. Pregnancy**

Any female subject who becomes pregnant during the course of the study should have BCX9930 discontinued immediately and must be followed through the end of the pregnancy. While pregnancy is not considered an AE, all cases of fetal drug exposure via the parent as a study participant (including partners of study participants) are to be reported immediately to BioCryst or its designee. Consent from study partners who become pregnant will be obtained prior to reporting any details of the pregnancy. Information related to the pregnancy must be given on a “Pregnancy Notification and Outcome” form that will be provided by the sponsor or its designee so that the pregnancy may be followed, and an outcome determined. Any AEs or SAEs experienced by a pregnant subject are to be reported as directed in Section 12.4.1.

Any complications reported in a subject’s pregnant partner should be reported on the Pregnancy Notification and Outcome form. All pregnancies must be followed to outcome, which occurs when an infant is delivered (live or still born), there is fetal demise, or there is an abortion (spontaneous or induced). Abortion (spontaneous or induced), fetal demise, and still birth, along with congenital abnormalities in the newborn, should be reported as separate SAEs.

### **12.5. Adverse Event Management**

The investigator (or qualified designee) will grade clinically significant events and laboratory abnormalities (if considered AEs) as detailed in Section 12.2. Grade 3 and Grade 4 clinically significant laboratory abnormalities should be confirmed by repeat testing and before any contemplated study drug/IMP discontinuation, unless such a delay is not consistent with good medical practice.

#### **12.5.1. Potential Drug-induced Liver Injury: Monitoring, Evaluation, and Discontinuation Criteria**

All treatment-emergent ALT elevations  $> 3 \times \text{ULN}$  should be confirmed, preferably within 72 hours, with repeat assessment of ALT, AST, total bilirubin, ALP, prothrombin time/INR, and complete blood count with differential. These may be repeated at a local laboratory as long as the results are reported to the investigator when available and the investigative site contacts the subject to ascertain any symptoms.

Subjects with ALT elevation  $> 3 \times \text{ULN}$  must be assessed to determine whether study drug must be withheld or discontinued. In addition, any potentially contributing medications, supplements, or over-the-counter medications that are not medically necessary should be discontinued if medically feasible.

Discontinuation of treatment should be considered for any of the following, and should be discussed with the sponsor medical monitor prior to BCX9930 discontinuation, considering the benefit-risk of discontinuing BCX9930:

- ALT or AST  $> 8 \times \text{ULN}$
- ALT or AST  $> 5 \times \text{ULN}$  for more than 2 weeks
- ALT or AST  $> 3 \times \text{ULN}$  and (total bilirubin  $> 2 \times \text{ULN}$  [unless there is evidence that the increase in bilirubin is due to hemolysis or Gilbert's syndrome] or INR  $> 1.5 \times \text{ULN}$  in the absence of warfarin therapy)
- ALT or AST  $> 3 \times \text{ULN}$  with the appearance of fatigue (over baseline fatigue), nausea, vomiting, right upper quadrant pain or tenderness, fever, rash, and/or eosinophilia ( $> 5\%$ )

If subjects are asymptomatic with no other pertinent laboratory abnormality, study drug may be continued under close observation. Transaminases, total bilirubin, ALP, and INR should be repeated at least twice weekly. Frequency of retesting can decrease to once per week or less if abnormalities stabilize or the study drug has been discontinued and the subject is asymptomatic. Additionally, several other items should be considered, including obtaining a more detailed history of symptoms and prior or concurrent diseases; obtaining a history of concomitant use of nonprescriptive medications, herbal and dietary supplements, alcohol intake, recreational drug use, or special diets; evaluation for acute viral hepatitis A, B, C, D, and E and potentially other serologies; evaluation for others as clinically indicated including alcoholic and autoimmune hepatitis, non-alcoholic steatohepatitis (NASH), and biliary tract disease.

The above criteria will be applied to increases in AST unless there is evidence that the increase is due to hemolysis. If both ALT and AST are elevated, subjects will be managed based on their ALT level, regardless of whether their AST increase is thought to be due to hemolysis.

If Hy's Law criterion is met and is assessed as probably or definitely related per treatment discontinuation criterion in Section 7.4.1, then study drug must be discontinued. Prior to discontinuation from study drug/BCX9930, the investigator should contact the sponsor medical monitor for a discussion regarding the event and assessment. If medically indicated, the investigator can discontinue the subject immediately and follow up with the sponsor within 24 hours.

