- Subjects should be asked to contact the investigator if they experience any new or worsening signs or symptoms of hemolysis. Subjects should be evaluated per the investigator's medical judgement. A review of dosing compliance to ensure that the subject is taking the drug should be performed, regardless of the method used to evaluate the subject (ie, in-person or remote assessment). It should also be determined whether the subject has had any recent complement-activating conditions (eg, infection, trauma, or surgery) that may have contributed to the hemolytic event.
- Treatment with BCX9930 should not be interrupted or withheld unless there is an absolute contraindication for continued dosing. Suggestions for anti-emetic therapy for subject with active nausea and vomiting when tablet contents are vomited are given in Section [9.6.2](#).

The sponsor medical monitor should be notified in the event of hemolysis symptoms, any planned treatment interruption, or permanent discontinuation of BCX9930. Any missed doses, treatment interruption, or permanent discontinuation must be recorded in the eCRF and source documents, including the reason for the interruption, missed doses, or discontinuation.

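### Protocol 12.5.1: managing on ALT alone when both enzymes are raised contradicts the rule that a non-hemolytic AST rise counts (minor; a wording clarification is enough)

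*Protocol*

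**What the plan says.** Protocol Section 12.5.1 contains these rules, in this order.

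- An ALT above 3 x ULN "should be confirmed, preferably within 72 hours, with repeat assessment of ALT, AST, total bilirubin, ALP, prothrombin time/INR" and a blood count. A subject with such an ALT "must be assessed to determine whether study drug must be withheld or discontinued".
- "Discontinuation of treatment should be considered for any of the following", followed by four criteria, each worded for ALT or AST: (1) > 8 x ULN; (2) > 5 x ULN for more than 2 weeks; (3) > 3 x ULN with raised bilirubin or INR, subject to stated exceptions; (4) > 3 x ULN with listed symptoms and/or eosinophilia.
- "If subjects are asymptomatic with no other pertinent laboratory abnormality, study drug may be continued under close observation", with retesting at least twice weekly.
- For AST, the section says: "The above criteria will be applied to increases in AST unless there is evidence that the increase is due to hemolysis".
- The sentence directly after that one reads: "If both ALT and AST are elevated, subjects will be managed based on their ALT level, regardless of whether their AST increase" (the remaining words refer to a hemolytic cause).
- If Hy's Law is met and the event is judged probably or definitely related, study drug must be stopped.

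**The concern.** The sentence applying the criteria to AST keeps a non-hemolytic AST rise in play. The sentence after it sets AST aside whenever both enzymes are elevated, and says this holds whether or not the AST rise is hemolytic. Its likely purpose is narrower: calling the AST rise hemolytic should not excuse a raised ALT. As worded, it also discards the non-hemolytic AST rise that had just been kept.

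The result can run backwards. A subject with a high non-hemolytic AST and a normal ALT meets a criterion. A subject with the same AST and a mildly raised ALT, which is the worse liver profile, may meet none. What is at stake is a written prompt to consider stopping drug, in a study where safety monitoring is one of two objectives.

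**Working it through.** There is no plan figure to reproduce; the check is a decision table built from Section 12.5.1.

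**Rule as written.** Let T be the threshold meant by elevated. If ALT > T and AST > T, only ALT is tested against criteria 1 to 4. Otherwise ALT is tested, and AST is tested too unless there is evidence of hemolysis. The section does not give T, so both T = 1 x ULN and T = 3 x ULN were tried.

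**Test case.** AST is 9 x ULN and non-hemolytic. Entries are the criteria met. "Alone" is replaced here by the column label *enzymes only*, meaning a single value with no other finding. *All findings* means more than 2 weeks' duration, the bilirubin/INR condition and symptoms together.

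| ALT (x ULN) | T = 1, enzymes only | T = 1, all findings | T = 3, enzymes only | T = 3, all findings |
|---|---|---|---|---|
| up to 1 | 1 | 1, 2, 3, 4 | 1 | 1, 2, 3, 4 |
| > 1 to 3 | none | none | 1 | 1, 2, 3, 4 |
| > 3 to 5 | none | 3, 4 | none | 3, 4 |
| > 5 to 8 | none | 2, 3, 4 | none | 2, 3, 4 |
| > 8 | 1 | 1, 2, 3, 4 | 1 | 1, 2, 3, 4 |

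With T = 1, the > 1 to 3 row is empty because the lowest enzyme cut-off in any criterion is > 3 x ULN and only ALT counts.

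**Where the AST half of each criterion is lost.**
- T = 1: ALT > 1 to 8 (criterion 1), > 1 to 5 (criterion 2), > 1 to 3 (criteria 3 and 4).
- T = 3: ALT > 3 to 8 (criterion 1), > 3 to 5 (criterion 2). Nothing is lost for criteria 3 and 4, since an ALT above 3 satisfies their enzyme part itself.

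**Illustrative grid.** The values are assumptions chosen to straddle the cut-offs: AST 3.5, 6, 9; ALT 0.9, 1.2, 2, 2.9, 3.5, 4.5, 5.5, 7, 8.5; duration, bilirubin/INR and symptoms each yes or no. That is 3 x 9 x 8 = 216 non-hemolytic profiles.
- Either enzyme counted: 21 of 24 meet a criterion at each of the six ALT levels from 0.9 to 4.5, 22 at each of 5.5 and 7, and 24 at 8.5. Total 6 x 21 + 2 x 22 + 24 = 194.
- T = 1: all 21 are lost at each of ALT 1.2, 2 and 2.9 (63). A further 3 are lost at each of 3.5 and 4.5, and 1 at each of 5.5 and 7 (8). Total 63 + 8 = 71 of 194.
- T = 3: only those 8 are lost, all at ALT > 3 x ULN.

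The 63 restate the empty row at three chosen ALT values. These are counts of rule outcomes, not of patients.

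**The case against.** The best defence is about the meaning of elevated. Where Section 12.5.1 earlier uses an ALT elevation as a trigger for action, it attaches > 3 x ULN. Carried forward, that closes the gap at ALT > 1 to 3 x ULN. This reading is available, but the opposite inference is just as fair: the section states the cut-off when it means it, and here it does not. Even at > 3 x ULN the reversal survives between ALT 3 and 8 x ULN, although the required assessment applies there.

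A second defence is that anchoring on ALT is sensible in PNH. Section 11.4 lists AST among the common PNH laboratory measures, and Section 12.5.3 warns of severe hemolysis after permanent discontinuation. That justifies ALT-only management when hemolysis explains the AST rise. It does not explain setting aside an AST rise that the preceding sentence says should count, and that sentence already requires the judgement about hemolysis.

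A third defence is that other safeguards remain, and this stands:
- the mandatory Hy's Law stop, which is not worded by ALT level, though no enzyme cut-off is given with it and it depends on the relatedness judgement;
- interruption or dose reduction for events potentially related to drug (Section 9.4.1);
- discontinuation for an unacceptable drug-related event (Sections 5.3 and 7.1);
- "Grade 3 and Grade 4 clinically significant laboratory abnormalities should be confirmed by repeat testing" (Section 12.5);
- stopping in the subject's best interest (Section 7.4.1).

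In addition, continued dosing under close observation is offered only to asymptomatic subjects with no other pertinent laboratory abnormality.

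A reader might infer more than the documents support, in three ways.
- That the sentence also removes the 72-hour confirmation and the required assessment. Both are tied to ALT > 3 x ULN, so they are equally absent at normal ALT and form no part of the reversal.
- That Section 12.5.3 makes continued dosing the general default: "Treatment with BCX9930 should not be interrupted or withheld unless there is an absolute contraindication for continued dosing". That bullet concerns hemolysis risk and leads into anti-emetic advice, while Section 9.4.1 expressly permits interruption for adverse events.
- That 71 of 194 indicates how often subjects would be affected. The grid was chosen by hand and cannot say.

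**Conclusion.** The contradiction is real: for a non-hemolytic AST rise with both enzymes elevated, two adjacent sentences give different answers. The size depends on an undefined word. On the > ULN reading, none of the four criteria can be met at ALT > 1 to 3 x ULN however high the AST. On the > 3 x ULN reading, the loss is confined to ALT > 3 to 8 x ULN, where assessment is already mandatory. Both results assume that managing on ALT overrides the AST half of the criteria, which is the plain sense of the sentence.

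The practical effect is minor. What is lost is a prompt to consider stopping, and the remaining safeguards would let a careful investigator act. The documents do not support reading this as a group of subjects left without liver oversight. No planned summary is defined by these criteria: the SAP's hepatic table (Section 8.2.2.4) uses a MedDRA search, and Protocol Section 13.3.4 uses fold elevations above ULN. This is a low-priority wording clarification.

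**What to change.** Keep the sentence that applies the criteria to AST, including its evidence standard for hemolysis. Replace the sentence after it with:

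*Evidence of hemolysis does not excuse a raised ALT. If both enzymes are raised and there is evidence that hemolysis explains the AST rise, the subject is managed on the ALT level. Otherwise the criteria apply to ALT or AST, whatever the ALT level.*

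With this wording elevated needs no threshold. All 194 grid profiles keep their criterion, because every one is non-hemolytic. AST rises with evidence of hemolysis are handled as now, on ALT only; this follows from the wording, as the grid does not test it.

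The cost is one replaced passage or a clarification memo, and possibly a few more discussions with the medical monitor. No extra tests are mandated.

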## 7.4. Individual and Study Termination Criteria

#### 7.4.1. Subject Withdrawal from Study Treatment

A subject will be permanently discontinued from BCX9930 for any of the following reasons:

- Invasive meningococcal infection or invasive encapsulated bacterial infection. Discontinuation of BCX9930 may occur after subject stabilization to prevent uncontrolled hemolysis.
- In the investigator's opinion, it is in the best interest of the subject to discontinue from further dosing.
- Subject noncompliance (eg, protocol deviation), as assessed by the sponsor or investigator, to be detrimental to study or subject benefit-risk profile.
- In the opinion of the investigator or sponsor, the subject is no longer receiving meaningful clinical benefit from continued treatment with BCX9930, or the subject qualifies for treatment with an available alternative therapy for PNH.
- Subject pregnancy
- Discontinuation at the request of the sponsor, relevant competent authority, or the governing institutional review board (IRB), research ethics board (REB), or independent ethics committee (IEC), collectively referred to as "ethics committee".

The reason for discontinuation of study treatment will be recorded in the source documents and electronic case report form (eCRF).

Subject who discontinue treatment with BCX9930 will not be allowed to re-enroll in the study or restart treatment with BCX9930 at a later date following a change in circumstances (eg, after a pregnant subject delivers her baby or a subject discontinues alternative therapy for PNH, including after completion of or discontinuation from a clinical study of another investigational agent for PNH).

Subjects who discontinue study drug for any reason will be monitored for hemolysis as described in Section 12.5.3.

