## **8.3. Subject Withdrawal**

Participation in the study is strictly voluntary; a subject may withdraw consent to contribute additional study information at any point. Subjects have the right to withdraw from the study at any time and for any reason. In addition, a subject's participation may be terminated for any of the reasons described in Section [7.4.1](#). Whenever possible, the investigator will consult with the sponsor medical monitor before halting a subject's participation in the study.

Although a subject may withdraw from the study at any time without specifying a reason for withdrawal, the reason for withdrawal, if provided by the subject, will be recorded in the subject's medical records (source documents) and also in the eCRF. If the reason for subject withdrawal is not known, attempts to contact the subject must be documented to establish whether the reason was due to an AE, and if so, this must be reported in accordance with the procedures outlined in Section [12.4.1](#). Vigorous attempts will be made for follow-up of all subjects who miss a study visit, given the potential for hemolysis if BCX9930 dosing is interrupted. If at any point in the study the clinic is unable to contact the subject after appropriate attempts have been made, the subject will be considered lost to follow-up. If a subject's participation in this study is terminated, the responsible investigator/clinical staff member will document termination in the source documents.

Unless consent is withdrawn, subjects who discontinue study treatment will be monitored for potential hemolysis and may be required to return to the clinic for an additional visit(s) to assess for acute symptomatic hemolysis, if and when symptoms occur. A dose tapering schedule should be considered (Section [9.4.2](#)). An early termination (ET) visit will be completed approximately 3 weeks after the date of last dose of BCX9930 (see [Table 2](#)).

Once subjects have withdrawn from the study, the sponsor will no longer provide treatment through the study.

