## **9.6. Missed Doses and Special Considerations for Dosing**

If BCX9930 needs to be withheld (eg, to assess a potentially drug-related TEAE), the investigator should consider the potential for hemolysis as described in Section [12.5.3](#).

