### 12.3. Relationship to Study Drug

An investigator who is qualified in medicine must make the determination of relationship to the study drug/IMP for each AE (not related, unlikely related, possibly related, probably related, definitely related). The investigator should decide whether, in his or her medical judgment, there is a reasonable possibility that the event may have been caused by the investigational product. If no valid reason exists for suggesting a relationship, then the AE should be classified as “not related”. If there is any valid reason, even if undetermined, for suspecting a possible cause-and-effect relationship between the study drug/IMP and the occurrence of the AE, then the AE should be considered “related”.

Not Related:	The event can be readily explained by other factors such as the subject's underlying medical condition, concomitant therapy, or accident, and no temporal relationship exists between the study drug/IMP and the event.
Unlikely Related:	The event does not follow a reasonable temporal sequence from drug administration and is readily explained by the subject's clinical state or by other modes of therapy administered to the subject.
Possibly Related:	There is some temporal relationship between the event and the administration of the study drug/IMP and the event is unlikely to be explained by the subject's medical condition, other therapies, or accident.
Probably Related:	The event follows a reasonable temporal sequence from study drug/IMP administration, abates upon discontinuation of the study drug/IMP, and cannot be reasonably explained by the known characteristics of the subject's clinical state.
Definitely Related:	The event follows a reasonable temporal sequence from study drug/IMP administration, follows a known or suspected response pattern to the study drug/IMP, is confirmed by improvement upon stopping the study drug/IMP (dechallenge), and reappears upon repeated exposure (rechallenge, if rechallenge is medically appropriate).

If the relationship between the (S)AE and the investigational product is determined to be “possible”, “probable”, or “definite”, the event will be considered to be related to the study drug/IMP for the purposes of expedited regulatory reporting (as applicable per country-specific regulatory requirements).

The sponsor may upgrade causality if deemed appropriate.

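### The mandatory Hy's Law stop in Protocol Section 12.5.1 cites a criterion that Section 7.4.1 does not contain, and both causality grades that trigger it include, in Section 12.3, improvement after stopping drug as one required element.

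*Protocol*

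**What the plan says.** Three sections of the protocol bear on the point.

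- **Section 12.5.1** (potential drug-induced liver injury) gives a list of laboratory and symptom findings for which stopping is to be considered. It then states a mandatory rule: if Hy's Law is met and the event "is assessed as probably or definitely related per treatment discontinuation criterion in Section 7.4.1, then study drug must be discontinued".
- **Section 7.4.1** (withdrawal from study treatment) opens with "A subject will be permanently discontinued from BCX9930 for any of the following reasons" and lists six. Section 8.3 sends the reader to the same list, saying that a subject's "participation may be terminated for any of the reasons described in Section" 7.4.1.
- **Section 12.3** (relationship to study drug) defines five causality grades. An event is probably related if, among other things, it "abates upon discontinuation of the study drug/IMP, and cannot be reasonably explained by the known characteristics" of the subject's clinical state. It is definitely related if, among other things, it "is confirmed by improvement upon stopping the study drug/IMP (dechallenge), and reappears upon repeated exposure", the last part applying where rechallenge is medically appropriate. The section also asks the investigator for a medical judgement on whether "there is a reasonable possibility that the event may have been caused by the investigational product".

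**The concern.** A rule that obliges the investigator to stop drug should be usable as written, and this one has two drafting problems. The reader who follows its cross-reference does not find the criterion it names. And the grade needed to trigger the stop includes, by the protocol's own definition, information that exists only after drug has been stopped or held.

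It is the only liver-specific rule in the visible text that requires an individual subject's drug to be stopped. If its condition can be read in two ways, two sites could treat the same event differently: one as a mandatory permanent stop, the other as a matter of judgement. Section 12.5.3 warns of severe hemolysis after permanent discontinuation, so an error in either direction would matter. Whether a stop is obligatory should not depend on how strictly a site reads a definition.

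**Working it through.** No arithmetic beyond counting applies. The check sets the sections side by side.

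**Step 1: does Section 7.4.1 contain the cited criterion?** Its six reasons are, in short:

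1. invasive bacterial infection of the kinds named;
2. the investigator's opinion that "it is in the best interest of the subject to discontinue from further dosing";
3. noncompliance;
4. no meaningful benefit, or an alternative therapy for which the subject qualifies;
5. pregnancy;
6. a request by the sponsor, an authority or an ethics committee.

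Matches to a liver, Hy's Law or causality-grade criterion: 0 of 6. The nearest is reason 2, a general opinion clause that names no laboratory finding and no grade. Redaction does not explain the gap: Section 7.4.1 shows no redaction mark. The nearby redacted text is in Section 7.4.2, which concerns termination of the study or a site.

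**Step 2: can the triggering grades be assigned while dosing continues?**

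| Grade in 12.3 | Improvement after stopping is a required element | Triggers the 12.5.1 stop |
|---|---|---|
| Not related | No | No |
| Unlikely related | No | No |
| Possibly related | No | No |
| Probably related | Yes, joined to the other elements by *and* | Yes |
| Definitely related | Yes, plus rechallenge where appropriate | Yes |

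The 2 grades that trigger the stop are the 2 that require a response to stopping. The other 3 do neither. Under the literal definitions, the number of triggering grades assignable during uninterrupted dosing is 0.

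**Step 3: does the protocol supply the missing interruption?** Three places provide for a hold:

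- Section 9.4.1 permits interruption for events potentially related to drug.
- Section 9.6 contemplates it: "If BCX9930 needs to be withheld (eg, to assess a potentially drug-related TEAE").
- Section 12.5.1 requires, for ALT above 3 × ULN, an assessment of whether drug has to be withheld or stopped. It requires the assessment, not the hold.

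Of these 3, 0 require a hold for a liver event. This count covers visible text only. Section 10.3.1, whose heading covers renal and hepatic safety monitoring, has redacted text before its procedure list. Section 10.1 and footnote b of Table 2 also have redactions concerning additional monitoring or assessments. Any of these might contain a relevant instruction.

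**Step 4: what other stops remain?** The Synopsis (Duration of Treatment) and Sections 5.3 and 7.1 say that treatment ends for an unacceptable drug-related adverse event. Section 7.4.1 has the best-interest reason. Section 12.5.1 has its list for consideration and also lets the investigator stop at once if medically indicated, telling the sponsor within 24 hours. All of these rest on judgement, so none repairs the one specific rule.

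**The case against.** The strongest reply is that the defect changes little in practice.

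- *The rule stands without its citation.* Section 12.5.1 states both the condition and the consequence, so a reader who finds nothing in 7.4.1 still knows what is required. This is largely right for the cross-reference taken alone. It does not answer the difficulty with the grades.
- *Causality is a judgement.* Section 12.3 puts medical judgement first, and the strict reading would bar a probable or definite grade for any event during uninterrupted dosing, not only a liver event. This is a fair point and limits the concern: investigators may well not apply the definitions strictly. But the text does not say which reading governs, and here a mandatory action depends on the answer.
- *There are central checks.* Section 12.3 lets the sponsor upgrade causality, in a sentence not expressly confined to expedited reporting. Section 12.5.1 directs sites to discuss discontinuation with the medical monitor. Both reduce the chance that sites diverge. Neither says how the 12.3 definitions are to be read for this rule.
- *Hold first, then stop, is coherent.* Resumption under Section 9.4.1 is allowed, not required, so a specific rule may override it. This stands: there is no contradiction with Section 9.4.1. What is missing is any visible statement that this sequence is intended.

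A reader might also cite Section 12.5.3, which says that dosing is not to be interrupted without an absolute contraindication, as ruling out a liver hold. That sentence belongs to the hemolysis section, and reading it so widely would conflict with Sections 9.4.1, 9.6 and 12.5.1. At most, it means that a prior hold cannot be assumed.

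**Conclusion.** The point holds in a limited form. The cross-reference failure is certain: 0 of 6 reasons match and no redaction accounts for it. The conflict with Section 12.3 is real on a literal reading: both triggering grades include improvement after stopping drug, as one element among several, so the mandatory stop could act only after a hold or other interruption. That conclusion assumes that the definitions are applied as written and that the redacted text contains no hepatic hold instruction.

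The consequence is possible inconsistent application of the only visible liver-specific mandatory stop. The documents give no basis for estimating how many subjects would be affected.

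Three stronger readings are tempting and are not supported. A reader might infer that subjects have no effective stop for liver injury; the judgement-based routes in Step 4 contradict that. A reader might infer that the rule can never operate; it can, after any interruption, or at any time if investigators grade by overall judgement. A reader might infer that the protocol requires no hold for a liver event anywhere; the redactions in Section 10.3.1 prevent that claim.

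**What to change.** Reconcile Sections 7.4.1, 12.3 and 12.5.1 in two respects:

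1. make the cross-reference in Section 12.5.1 point to a criterion that exists;
2. make the causality condition in Section 12.5.1 consistent with the grade definitions in Section 12.3, so that every site can tell when the condition is met.

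Which clinical rule should apply, and at which grade, is for the sponsor's medical team; nothing here argues for one version. The cost is protocol wording or a clarification letter to sites. It needs no new procedures, visits or data.
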